PFS24 and other survival endpoints will also be calculated for the registry arm patients. For both interventional arm and registry arm, start date for these endpoints will be date of study entry. The registry arm PFS24 will serve as an internal check on the historical controls’ PFS24 estimate, but there is no plan to formally compare the interventional arm and registry arm PFS24 due to lack of statistical power for this comparison.

If observed DLT rate is 33.3% (14/42) or more, 95% confidence interval for DLT rate would be 21.0-48.4% or more, the true DLT rate is very likely to be >20% and we would recommend to the DSMC that study enrollment be stopped.

If observed DLT rate is in between these values (9 to 13 out of 42), it is consistent with a range of true DLT rates that includes both safe and unsafe rates. In this case, we will ask the DSMC to make a decision about whether to continue or stop enrollment.

Other secondary endpoints

Adverse events will be tabulated by organ system and severity. Proportions of patients with adverse events will be estimated with 95% confidence intervals.

Plasma biomarkers (e.g. cell free DNA level) will be summarized using medians and interquartile ranges; changes in biomarkers will be assessed using the Wilcoxon signed rank test. Correlation of biomarkers with radiographic response will be evaluated using a Wilcoxon rank sum test on patients with and without the event of interest. If feasible, these analyses will be supplemented by more formal analyses with the Cox model.

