9. STUDY CALENDAR

This study calendar is for patients enrolled in the interventional arm who will receive radiation therapy on study. For patients in the separate registry arm, clinic visits,

laboratory draws, and scans will be per standard of care and are not mandated to be on a specific schedule. For interventional arm patients, after disease progression or unacceptable toxicity, the patient enters the long-term follow-up period and visit/imaging schedule will be at the discretion of the treating medical oncologist and not mandated by the study.

All treatment and evaluation items in the study calendar are part of standard medical care, except for the peripheral blood biomarker lab draw which is a research procedure. Also, if a patient has pre-radiation CT-guided biopsy or fiducial placement for routine clinical purposes, research cores may be obtained during that procedure.

Action	Pre Entry ¹	Pre-RT	Day 1 of RT	Last day of RT	8 weeks after sim ²	16 weeks after sim ²	24 weeks after sim ²	36 weeks after sim ³	48 weeks after sim ³	Every 12 weeks until disease progression or unacceptable toxicity ³	After disease progression or unacceptable toxicity
History & Physical Exam	X				X	X	X	X	X	X ¹¹	
ECOG PS	X				X	X	X	X	X	X ¹¹	
Labs											
CBC/diff.	X ⁹										
CMP	X ⁹										
CT Thorax (Chest), or PET/CT	X				X	X	X	X	X	X ¹¹	
Brain MRI or CT, if known brain metastases	X				X	X	X	X	X	X ¹¹	
Vital status evaluation					X	X	X	X	X	X	X ¹⁰
Study consent		X ¹²									
Toxicity evaluation		X			X	X	X	X	X	X ¹¹	
Fiducial placement (as clinically indicated)		X									
Research cores during fiducial placement (optional)		X									
Radiation therapy			X	X							
Lesion measurements				X ⁴	X ⁵	X ⁵	X ⁵	X ⁵	X ⁵	X ⁵	

Peripheral blood biomarkers (if consented for this portion of study)			X ⁶	X ⁷	X ⁸						
--	--	--	----------------	----------------	----------------	----------------	----------------	----------------	----------------	----------------	--

Sim=simulation

¹ Within 4 weeks prior to enrollment

² +/- 2 weeks

³ +/- 4 weeks

⁴ After the last day of RT or up to 4 weeks following the completion of RT: For each radiation treated lesion, document diameter on sim CT, location and radiation dose.

⁵ Document size of each radiation treated lesion. Also document RECIST response compared to radiation SIM CT. For follow-up time points starting with 108 weeks: if imaging studies were not performed, lesion measurements are not required.

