⁶ Blood drawn before first fraction of RT or any time up to 14 days before first fraction.

⁷ Blood drawn after last fraction of RT or any time up to 14 days after last fraction.

⁸ Optional

⁹ Labs collected prior to study and prior to each cycle of immunotherapy at the discretion of the treating medical oncologist.

¹⁰ After disease progression/unacceptable toxicity, vital status will be recorded every 6-12 months by chart review and/or telephone calls.

¹¹ Adverse events will be recorded until the 96-week follow-up visit. Starting with the 108-week follow-up visit, adverse events will not be recorded, and the history & physical exam, ECOG PS, and imaging studies will all be optional.

¹² Within 60 days prior to first dose of study radiation therapy

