10.2 Secondary outcome #1

Title: Acute (0-6 months) and late (>6 months) grade 3-5 toxicity

Time frame: 0-4 years after study entry

Safety issue: yes

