10.2.1 Relevant Subset

Patients who enroll on the interventional arm and receive radiation therapy on protocol will be analyzed.

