10.2.4 Measurement Time Points

Follow-up clinic visits at 8 week intervals (± 2 weeks) for the first 24 weeks, and then at 12 week intervals (± 4 weeks) until disease progression.

If there is RECIST 1.1 disease progression or unacceptable toxicity, the patient will be considered to be off of protocol therapy and will not be required to be seen at protocol specified follow up time points. The patient will then be followed for survival outcomes collected during standard of care visits, with study data collection typically occurring every 6-12 months. If the patient is lost to follow-up and not seen at Stanford, phone calls will be performed to check for survival status annually.

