10.6.4 Measurement Time Points

Follow-up clinic visits at 8 week intervals (± 2 weeks) for the first 24 weeks, and then at 12 week intervals (± 4 weeks) until disease progression or unacceptable toxicity.

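### Late grade 3-5 toxicity and DLT are declared over 0-4 years in all irradiated patients, but recording stops at week 96 and scheduled assessment at progression, so unrecorded late events can only lower the rates

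*Protocol*

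**What the plan says.** All references are to the Protocol.

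- **Window.** Section 10.2 sets "Time frame: 0-4 years after study entry" for grade 3-5 toxicity, and Section 10.6 sets the same for DLT. Section 10.2.2 defines late toxicity as anything beyond 6 months from the first radiation day, with no upper limit.
- **Population.** Section 10.2.1: "Patients who enroll on the interventional arm and receive radiation therapy on protocol will be analyzed". Section 10.6.1 takes everyone with at least one radiation dose.
- **Estimate.** Section 12.2.2: "Proportions of patients with adverse events will be estimated with 95% confidence intervals". The interim DLT rate is a count out of 42.
- **End of recording.** Section 9, footnote 11: "Adverse events will be recorded until the 96-week follow-up visit". From the 108-week visit on, none are recorded.
- **End of scheduled assessment.** Under Section 10.6.4, DLT visits run "until disease progression or unacceptable toxicity"; Section 10.2.4 has the same effect for grade 3-5 toxicity. After that point, Section 9 says, the "visit/imaging schedule will be at the discretion of the treating medical oncologist and not mandated by the study".
- **What is collected afterwards.** Section 10.2.4: "The patient will then be followed for survival outcomes collected during standard of care visits". Footnote 10: "vital status will be recorded every 6-12 months by chart review and/or telephone calls". The calendar's last column marks nothing else.
- **Other routes.** Sections 10.2.3 and 10.6.3 add follow-up for hospital admissions and other medical events, without a duration. Section 7.2 covers serious adverse events up to 6 months after radiation ends, and not once progression or unacceptable toxicity has moved the patient to long-term follow-up.

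**The concern.** The declared window and the recording rules do not fit together. A patient who is alive but no longer assessed counts as event-free in a simple proportion over all irradiated patients. Patients with an earlier recorded event are not lost. What is lost is a first late toxicity or DLT that occurs after week 96, or after scheduled visits have ended, and reaches no record. Acute toxicity is exposed only in patients whose scheduled visits end before 6 months.

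This matters because radiation toxicity became the main safety question after a fatal pneumonitis (Section 12.2.2). Section 4.3.7 lists pneumonitis, hemoptysis and large airway necrosis among subacute or late effects. Section 12.2.2 itself warns that one benchmark DLT rate counted first-year events only, so the protocol recognises that the counting window affects how a rate is read. Section 2.2 makes an acceptable toxicity rate a condition for going on to phase III. Events never recorded may not be recoverable at analysis, whatever a SAP says.

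**Working it through.** **1. What kind of rate is planned.** Reproduce the interim intervals with the Wilson score formula, z = 1.96, n = 42:

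centre = (p + z²/2n) / (1 + z²/n); half-width = z·√(p(1−p)/n + z²/4n²) / (1 + z²/n).

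- 8/42: p = 0.1905, centre 0.2164, half-width 0.1166, giving 10.0% to 33.3%. The protocol states 10.0-33.3%.
- 14/42: p = 0.3333, centre 0.3473, half-width 0.1372, giving 21.0% to 48.4%. The protocol states 21.0-48.4%.

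Both match. The DLT rate is therefore a crude proportion with every treated patient in the denominator and no allowance for follow-up time.

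**2. Declared window against recording.** 4 years = 4 × 365.25 / 7 = 208.7 weeks. Recording to week 96 covers at most 96 / 208.7 = 46%, leaving 208.7 − 96 = 112.7 weeks with none. (Week 96 counts from simulation and the 4 years from study entry; this small difference is ignored.)

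**3. When scheduled assessment ends.** Section 12.3 plans with a PFS24 of 35% (null) and 52% (alternative). By week 24 from entry, 1 − 0.52 = 48% to 1 − 0.35 = 65% have progressed or died. That is 42 × 0.48 = 20.2 to 42 × 0.65 = 27.3 of 42 patients, before the late period opens at about week 26. These are upper limits on the number alive after progression at week 24, because patients who died without toxicity are true non-events. The protocol does not give the split.

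**4. Which stop matters more (illustration; exponential PFS is an assumption).** PFS at week 96 = PFS24^(96/24): 0.35⁴ = 0.015 and 0.52⁴ = 0.073, or 0.6 to 3.1 of 42 patients still on scheduled assessment. On this reading the stop at progression removes far more assessment than the 96-week limit.

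**5. Direction.** Let c ≤ 1 be the share of patients with an event whose event is recorded. With a fixed denominator, the expected recorded rate is the true rate × c, which cannot exceed the true rate. For illustration, with c assumed at 0.9, 0.8 and 0.7, a true 35% would be recorded as 31.5%, 28.0% and 24.5%, and a true 20% as 18%, 16% and 14%. Nothing in the protocol says what c is. The 95% interval reflects sampling error only and does not cover this loss.

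**The case against.** Several points on the other side have weight.

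- **Severe events may still be found.** The follow-up for hospital admissions and other medical events is not said to end at progression. That stands as mitigation: it may shrink the loss. But it has no stated duration or post-progression route, and it does not override footnote 11.
- **Stopping at progression is a deliberate choice.** It is stated consistently, and attribution to radiation becomes harder once later therapy starts. That stands as a reason for the design. It does not support presenting the result as a 0-4 year rate in all irradiated patients.
- **The 4 years may be only an outer window.** Overall survival has the same one, and study completion is estimated for February 2023, so anyone enrolled after February 2019 cannot reach 4 years by then. This stands against reading 46% as a share of lost data, or calculating as if everyone were followed for 4 years. It does not remove the conflict, since no patient's events are recorded past the 96-week visit.
- **The estimator belongs in a SAP.** Largely fair: the absence of a cumulative-incidence estimate is not itself the fault. The collection rules are in the protocol and decide what any SAP can use.
- **Errors can also go upward.** Section 4.2.3 notes that immune-mediated pneumonitis can mimic radiation pneumonitis, so wrong attribution could add DLTs. This stands, and limits the directional claim to under-recording.

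**Conclusion.** The concern holds as an internal contradiction with a known direction. The protocol declares 0-4 year toxicity and DLT endpoints in all irradiated patients, while its recording rules support at most a window to week 96 or to progression or unacceptable toxicity, whichever comes first. Under-recording can only lower the reported proportions. This conclusion needs no survival model. The amount cannot be fixed from the protocol, and the coverage figures describe time and patients, not missed events.

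Three stronger readings are not supported:

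- A reader might infer that any error in these rates is downward. Attribution and sampling error can go either way.
- A reader might infer that the rates are known to be much too low. The capture fraction is unknown, and follow-up for hospital admissions may catch severe events.
- A reader might infer that the interim decision is compromised. Of a planned enrolment of at least 43, 42 had already been treated, and the DSMC makes the determination. One missed event would turn 8/42 into 9/42 (Wilson 11.7% to 35.9%), moving the count into the range left to the DSMC. That shows only how sensitive a boundary is to one event, not that an event was missed.

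The point concerns secondary safety endpoints and should be corrected. It does not touch the primary analysis.

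**What to change.** 1. Reconcile Sections 10.2 and 10.6 with footnote 11 of Section 9. Either restate the window that the data support (to week 96, or to progression or unacceptable toxicity if earlier), or extend recording to match 0-4 years.
2. Record grade 3-5 events attributed to study radiation after progression, at the chart reviews already planned every 6 to 12 months. State that the follow-up in Sections 10.2.3 and 10.6.3 continues then. Because Section 10.2.2 does not limit toxicity to radiation-attributed events, say so wherever later capture is limited to them.
3. Keep the simple proportions for comparison with the benchmark rates in Section 12.2.2, but label them with their actual ascertainment window. Beside them, report cumulative incidence from the first radiation day, with death as a competing event and numbers at risk. If item 2 is not adopted, note that censoring at progression may be informative.
4. Leave the 8/42 and 14/42 interim counts unchanged, and give the DSMC each patient's toxicity follow-up time beside them.

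The cost is one extra field at existing chart reviews and one added estimate. Attribution after later therapy will be less certain, and reported toxicity rates may rise.

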12.3 Sample Size Justification

The null hypothesis is that PFS24 for the interventional arm population will be the same as a similar population treated with immunotherapy alone without addition of radiation therapy. A null hypothesis PFS24 of 35% is assumed (see section 12.2). The alternate hypothesis is that the study patients' PFS24 is improved over historical controls, at 52%. The exact binomial test will be used to test this hypothesis. With one-sided alpha of 0.1 and at least 80% power, 39 evaluable patients are required. Assuming 10% dropout/unevaluable patients, total enrollment will be at least 43 patients.

12.4 Patient Accrual

[This section was not edited after the revised sample size was determined, but is left in place for historical documentation purposes.]

We anticipate that this study will take 2.5 years to accrue with another 6 months required for follow up. We estimate that an additional 30 patients will enroll on the companion registry study.

The yearly accrual estimate of 22 patients on the interventional arm is based on the monthly number of patients starting anti-PD-1/anti-PD-L1 immunotherapy at Stanford Cancer Center (data from Stanford Cancer Institute Research Database). Around 75 patients started these drugs over a 7 month period in 2016 (yearly rate of ~130 patients). We estimate that 70% of patients starting these drugs have stage IV NSCLC. Assuming that 50% of those patients are eligible for this study, and 65% agree to go on the interventional arm, yearly accrual would be 30 patients, a comfortable margin above our required 22 patient yearly accrual. Of the 35% of patients who do not agree to enroll in the interventional arm, if 75% of these patients agree to enroll on the registry arm, then total registry arm enrollment will meet the target of 30. Assuming 10% of these patients are lost to follow-up/unevaluable, 27 patients on the registry arm will be available for analysis.

12.5 Interim Analyses

There will be a single interim analysis for safety after at least 42 patients have received protocol treatment; see section 12.2.



Welsh J et al. Pembrolizumab with or without radiation therapy for metastatic non-small cell lung cancer: a randomized phase I/II trial. *J Immunother Cancer* 2020 Oct;8(2):e001001.

APPENDICES**APPENDIX A: Participant Eligibility Checklist**

Protocol Title:	Radical RADiotherapy and Immunotherapy for metastatic CAncer of the Lung (RRADICAL)
Protocol Number:	IRB 40088
Principal Investigator:	[name]

II. Subject Information:

Subject Name/ID:
Gender:  Male  Female

III. Study Information:SRC Approved IRB Approved Contract signed **IV. Inclusion/Exclusion Criteria**

Inclusion Criteria (From IRB approved protocol)	Yes	No	Window	Last day to Register	Supporting Documentation*
1. Has stage IV non-small cell lung cancer, or initially stage I-III disease with distant metastatic recurrence					
2. Age \geq 18					
3. Has been receiving anti-PD-1 or anti-PD-L1 immunotherapy for at least four weeks (refer to section 4.2.1)					
4. Has had restaging imaging after initiation of immunotherapy, at least 4 weeks after pre-immunotherapy baseline imaging. CT or PET/CT of at least chest/upper abdomen must be performed within 4 weeks prior to registration. For patients with history of brain metastases, brain MRI or CT is required within 4 weeks of registration; for other patients brain MRI or CT is required within 12 weeks of registration. Diagnostic PET/CT performed as part of radiation simulation can be used as the restaging imaging.					
5. Most recent imaging shows measurable disease as defined by RECIST 1.1					
6. Evaluation by a Stanford medical oncologist must show: 
 The patient is expected to continue on immunotherapy for at least three more months Imaging must show response, stable disease, or modest progression 					
					

c. If there is modest progression, the patient must be clinically stable in terms of performance status and overall disease-related symptoms					
7. Has at least one extracranial tumor safely treatable with radical-dose radiation therapy and that has not been previously treated with radiation					
8. ECOG performance status 0-2					
9. Has the ability to understand and the willingness to sign a written informed consent document.					
Exclusion Criteria (From IRB approved protocol)					
1. Untreated brain metastases, if not planned to be treated in this course of radiation therapy					
2. Pregnancy or women of childbearing potential not willing/able to use contraception during protocol treatment					

*All subject files must include supporting documentation to confirm subject eligibility. The method of confirmation can include, but is not limited to, laboratory test results, radiology test results, subject self-report, and medical record review.

Statement of Eligibility

By signing this form of this trial I verify that this subject is **eligible** / **Ineligible** for participation in the study. This study is approved by the Stanford Cancer Institute Scientific Review Committee, the Stanford IRB, and has finalized financial and contractual agreements as required by Stanford School of Medicine's Research Management Group.

Treating Physician Signature:	Date:
-------------------------------	-------

Printed Name:

Secondary Reviewer Signature:	Date:
-------------------------------	-------

Printed Name:

Study Coordinator Signature:	Date:
------------------------------	-------

Printed Name:

APPENDIX B: Protocol Pre-review Checklist

The protocols will be pre-reviewed prior to the assignment of an SRC meeting date in order to ensure that protocols contain all the required elements and information in the appropriate format. This Checklist is intended to be helpful in the protocol writing process.

Appendix B is not part of the protocol. Please delete it after completing the protocol.

Protocol Pre-review Checklist

No	Description	Yes	No
1	Protocol is in the appropriate template for either Interventional or Non-interventional study		
2	Title page includes names and addresses of Principal Investigator, Co-investigators, Biostatistician and Coordinator as appropriate		
3	Sponsor information is included if appropriate		
4	Title page includes protocol version and date		
5	Protocol document has page numbers		
6	Schema is legible		
7	List of Abbreviations is relevant to this protocol		
8	Table of contents is complete		
9	Instructions in the template are deleted		
10	Section titles are appropriately designated and numbered		
11	All the sections in the template are complete		
12	Study calendar is complete		
13	Protocol contains adequate background/rationale information		
14	Objectives and measurements of outcome are clearly stated		
15	The sections on objectives, eligibility, outcome measurements, statistics and study calendar are consistent		
16	Monitoring plan refers to Stanford DSMC		
17	Statistical section is appropriate for this study		
18	Appropriate references are included		
19	Protocol includes eligibility checklist		
20	Protocol includes questionnaires as needed		
21	Protocol includes CRF statement		
22	Protocol document is well organized		

Note: Some of the requirements are applicable to only **Interventional** studies as specified in the template.
